2. Compare the effectiveness of the two intervention sequences (1st cognitive training and 2nd mindfulness versus 1st mindfulness and 2nd cognitive training) on neurocognitive, biopsychological, biomarker, and connectome outcome variables.

METHODS

1. Study Design 3: In this single-center study (La Paz University Hospital), the pilot phase of a randomized, counterbalanced, crossover controlled clinical trial with a recycled waiting list will be conducted according to CONSORT standards. (Boutron et al., 2017).

2. Participants: A total of 40 patients (20 patients initially in the clinical trial phase and 20 on the waiting list) between the ages of 8 and 18 will be recruited from the three clinical groups in Study 1, requiring compliance with inclusion criteria (having a computer, mobile phone, or tablet with an Internet connection) and exclusion criteria (CI < 80 in Matrices). These 40 patients will be recruited from the sample participating in Study 1 using a strategic/intentional non-random sampling technique.

3. Outcome variables: In pre-/post-intervention phases, primary variables will be measured using performance tests: processing speed (SDMT); sustained visual attention (CPT-3); working memory, implicit, immediate/delayed auditory-verbal, visual-spatial, and intermodal [Clinical Memory Assessment (ECM)]; verbal fluency [Verbal Fluency Test (VFT)]; resistance to visual interference [Colors and Words Test (STROOP)]. Secondary variables in pre-/post-intervention phases are questionnaires measuring: executive functions [BRIEF-2, parent-completed version]; pain intensity and interference [BPI, self-reported by patient]; sleep quality [PROMIS and AIQ, self-reported by patient]; emotional and behavioral problems [BASC-3, parent and self-reported versions]; and mindfulness, trait level [Children and Adolescent Mindfulness Measure (CAMM)]; as well as biomarkers (inflammatory and immunological) and a neurofunctional analysis (connectome), using electroencephalogram (EEG) recordings. In the intermediate phase (3 months after the start of treatment), the BASC-3 questionnaire will be administered. Finally, at the 6-month follow-up after the end of both interventions, the BRIEF-2, BASC-3, BPI, AIQ, and PROMIS questionnaires will be included.

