4. Procedure: Participants will be randomized into two subgroups, which will be equally randomized into one of the following two intervention implementation sequences, according to an intragroup Latin square equal weighting technique (AB/BA design). (Fontes-de-Gracia et al., 2020): 1st sequence) Cognitive training (weeks 1-12) + Mindfulness-based emotional regulation (weeks 13-24); 2nd sequence) Mindfulness-based emotional regulation (weeks 1-12) + Cognitive training (weeks 13-24). This equal weighting technique will allow for systematic control of progressive error (order or period), without the need for a washout period between the two interventions, due to a potential residual or carry-over effect, as the treatments do not interfere with each other and are of a different nature (neurocognitive intervention versus emotional intervention).

Each intervention will last 12 weekly sessions, with a total sequence of 24 weeks for both treatments. The group of participants on the waiting list (control group) will remain there until after the 24 sessions, at which point they will begin the same process described above for randomization into subgroups and sequences for implementation of the interventions. Each treatment sequence will have a total of 10 participants assigned to it, in two age-differentiated groups (8-12 versus 13-18 years old), with 5 participants per group. Given this small sample size per group, in order to facilitate smooth interaction among participants, one of the pre-intervention scores (Emotional Regulation Index, BRIEF-2) will be used as a blocking variable, in addition to age, artificially dichotomized according to a cutoff point (resulting in low and high values on that index), thus maximizing the control of extraneous intergroup variables. Consequently, four subgroups of patients will be created by combining the levels of two blocking variables: age (8-12 versus 13-18 years) and Emotional Regulation Index score (low versus high values).

Subsequently, after assigning an anonymized code to each patient, using web-based randomization software, each treatment administration sequence (AB/BA) will be randomly assigned to each of the four patient subgroups.

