On the one hand, the cognitive training intervention will use the Sincrolab platform, which guarantees security and confidentiality and has been validated in clinical populations of children and adolescents (Medina et al., 2021). Four weekly sessions of 15 minutes each will be prescribed, training neurocognitive functions such as attention, memory, visuospatial skills, and executive functions. This platform provides regular reports on the use and fulfillment of objectives for each participant. In addition, once a week, online and also in the afternoon for 60 minutes, a group video call will be held with all participants to discuss difficulties and obstacles in using the platform, as well as to promote full adherence to the weekly usage guidelines. All these sessions will be moderated by the principal investigator of this project. In the event of less than 50% weekly adherence to the use of Sincrolab, the research team will make a weekly call to the participant and their legal guardians to encourage greater compliance. On the other hand, mindfulness-based emotional regulation interventions will be carried out in groups and online (video calls), following intervention protocols that have already been validated in children and adolescents in this online format (Pathrose et al., 2021). Each weekly session will last 60 minutes, with practice tasks prescribed for everyday contexts (four weekly tasks of 15 minutes each). To this end, a web repository will be used, with two versions differentiated by age range (children versus adolescents), from which material (comics and audio files for practicing mindfulness-based exercises) will be extracted to put emotional regulation skills into practice independently at home. The two interventions in each treatment sequence have the same duration and weekly workload for independent work. Each intervention implementation sequence will be preceded by a pre-intervention assessment, followed by an intermediate assessment before the change in treatment administration sequence, and ending with a post-intervention assessment (the same as the pre-intervention assessment). The connectome will be measured both at rest and during an activity (the neurocognitive assessment tests themselves) carried out by technical staff from an external company. Both the neurocognitive assessment and the connectome assessment will be carried out individually and in person at the hospital facilities, one month before the start of each treatment sequence. Biomarkers will be extracted from routine control tests. Finally, the questionnaires (for patients and their legal guardians) will be completed via electronic links from the publishers that market them (BRIEF-2 and BASC-3), as well as REDCap (BPI, PROMIS, AIQ, and CAMM).

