Finally, multiple regression analyses will be performed to predict post-treatment and 6-month follow-up measures (neurocognitive and biopsychological), coding some measures from Study 1 as predictors, such as: processing speed levels, sustained visual attention, verbal fluency, and resistance to visual interference.

6. Limitations, biases, and contingency plan: given that participant loss is expected in any clinical trial, additional participants from the previous study will be recruited in such a scenario. The multi-method evaluation approach used (objective neurocognitive tests, questionnaires, biomarkers, and connectome) will avoid the common method bias (Podsakoff et al., 2012). Anticipating the temporary limitation on pre-/post-intervention assessment tasks as a potential risk to implementation, the age-differentiated treatment editions will be implemented partially simultaneously, with a one-month delay in the start of the intervention for each age group, using that month for the pre-intervention assessment of the other group.

This project will be carried out in accordance with the ethical principles of the Fortaleza Declaration of Helsinki (2013), strictly respecting confidentiality and the requirements of Spanish/European data protection regulations, as well as the provisions of the biomedical research law (Law 14/2007, of July 3); the informed consent of patients and their legal guardians will be required.

Finally, given that the objectives of these studies have not been scientifically addressed to date in the child and adolescent population receiving CAR-T therapies, this project will make a novel, original, and relevant contribution at the scientific-clinical level, and is in line with one of the strategic lines of our institution, IdiPAZ, and its core hospital, given that it coordinates the **European Reference Network TransplantChild**.

DATA MANAGEMENT PLAN

The data management plan will include criteria for the handling and administration of scientific data following the FAIR principles (Findable, Accessible, Interoperable, and Reusable).

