INTELLECTUAL PROPERTY: The results of the project that may lead to new diagnostic techniques, modifications to existing treatments and/or protocols, medicines, medical devices, or vaccines will initially be communicated confidentially to the institution by the PI in order to determine whether they could be patentable or should be protected by intellectual property rights. The data may not be disclosed until the patents related to the research are protected, if any, or the appropriate measures are taken to protect the intangible assets.

WORK PLAN

The research team formally involved in this project consists of:

- Psychologists trained in neuropsychology to perform neurocognitive and biopsychological assessments and interpret their data: [name] ([name]) and [name] ([name])
- Hematologists/oncologists to refer participants to the project, record biomarkers, and medically interpret the results: [name] ([name]), [name] ([name]), [name] ([name]), [name] ([name]), and [name] ([name]).
- Teaching and research staff: [name] ([name]), expert in psychotherapeutic interventions; [name] ([name]), national reference for pain in children and adolescents and telemedicine; and [name] ([name]), expert in health technologies.
- Formal collaboration of a representative of the Spanish Association Against Cancer (citizen participation): [name] ([name]), to identify unmet needs during the care process.
- Additional citizen participation (non-formal collaborators) from ASION: [name] ([name]) and [name] ([name]); to identify unmet needs during the care process.

PROJECT DEVELOPMENT STAGES

- November-December 2025** (experimental group) and **July-August 2026** (recycled waiting list): Pre-intervention neurocognitive, biopsychological (conducted by psychologists), and connectome (conducted by an external company) assessment.
- March 2026-July 2026** (experimental group) and **September 2026-February 2027** (recycled waiting list): Cognitive training and mindfulness.
- July-August 2026** (experimental group) and **March-April 2027** (recycled waiting list): Post-intervention neurocognitive, biopsychological, and connectome assessment.
- December 2026** (experimental group) and **August 2027** (recycled waiting list): Biopsychological assessment at 6 months follow-up.

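### The work-plan calendar does not fit the 24 weekly sessions plus one-month stagger, and it places the experimental group's 6-month follow-up less than 6 months after the last session.

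*Protocol*

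**What the plan says.** **Methods (protocol).**
- Item 4 (Procedure): "Each intervention will last 12 weekly sessions, with a total sequence of 24 weeks for both treatments". The waiting list is held until those 24 sessions are over.
- Item 6 (Limitations, biases, and contingency plan) says that "the age-differentiated treatment editions will be implemented partially simultaneously". The stagger between the editions is described as coming "with a one-month delay in the start of the intervention for each age group". The month gained is to be used for pre-testing the other age group.
- Item 4 places the in-person neurocognitive and connectome pre-test "one month before the start of each treatment sequence".
- Item 3 (Outcome variables) sets the last questionnaires "at the 6-month follow-up after the end of both interventions".

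**Work plan, Project development stages (protocol).** The pre-test is in November-December 2025 for the experimental group and July-August 2026 for the recycled waiting list. The later stages are:
- Treatment is entered as "March 2026-July 2026 (experimental group) and September 2026-February 2027 (recycled waiting list): Cognitive training and mindfulness".
- The post-assessment runs over July and August 2026 in the first wave, and over March and April 2027 in the second.
- The final visit is entered as "December 2026 (experimental group) and August 2027 (recycled waiting list): Biopsychological assessment at 6 months follow-up".

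**Use in the analysis.** Item 5 (Statistical analyses) makes six months the third level of the repeated-measures factor in the 2x3 ANCOVA. It also makes the 6-month measures an outcome of the multiple regressions.

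**The concern.** The calendar and the Methods describe the same visits, but the dates cannot all be met. On the calendar's month names alone, July to December is 5 months and February to August is 6, so one label covers two intervals. The treatment window is shorter than the treatment, which puts the post-intervention dates in doubt as well.

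At stake is what the time points mean. A maintenance effect reported at six months would rest on visits made several weeks to several months earlier. If the printed post-assessment dates were followed literally, some patients could be assessed before their last session. The two waves would also carry different intervals from pre-test to treatment and from treatment to follow-up.

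**Working it through.** **Inputs.** Twenty-four weekly sessions and the stagger come from Methods items 4 and 6. Months come from Project development stages. The calendar gives months only, so days are assumed: each wave starts on the first day of its window, the delayed age group starts on the first day of the next month, and follow-up falls between the first and last day of its month. One month = 30.44 days. The span from first to last session is 23 x 7 = 161 days.

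**1. Does treatment fit?**
- Experimental window: 1 March-31 July 2026 = 153 days = 153/7 = 21.9 weeks. At most 1 + floor(152/7) = 22 weekly sessions fit.
- First age group: 1 March + 161 days = 9 August, 9 days past the window.
- Delayed age group: 1 April + 161 days = 9 September, 40 days past the window. This is after the July-August post-assessment period, and after a waiting-list start on 1 September.
- Waiting-list window: 1 September 2026-28 February 2027 = 181 days = 25.9 weeks. First age group: 1 September + 161 days = 9 February, which fits. Delayed group: 1 October + 161 days = 11 March, 11 days past the window.

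**2. How old is the follow-up?** First, the calendar's own end dates at face value:
- 31 July to 1-31 December 2026: 123-153 days = 4.0-5.0 months.
- 28 February to 1-31 August 2027: 154-184 days = 5.1-6.0 months.

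Then from the actual 24th session, with the same rule for both waves:

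| Wave and age group | Last session | Days to follow-up month | Months |
|---|---|---|---|
| Experimental, first | 9 Aug 2026 | 114-144 | 3.7-4.7 |
| Experimental, delayed | 9 Sep 2026 | 83-113 | 2.7-3.7 |
| Waiting list, first | 9 Feb 2027 | 173-203 | 5.7-6.7 |
| Waiting list, delayed | 11 Mar 2027 | 143-173 | 4.7-5.7 |

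**3. Can any March start reach 6 months by December?** No. The earliest start (1 March) and the latest follow-up (31 December) give 4.7 months, and a later March start only shortens this. A gap of 6.0 months needs a last session on 1 July, which is 122 days = 17.4 weeks after 1 March and cannot close a 24-week sequence.

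**4. Pre-test interval.**
- Experimental: 31 December 2025 to 1 March 2026 = 60 days = 8.6 weeks; 1 November 2025 to 1 March 2026 = 120 days = 17.1 weeks.
- Waiting list: 31 August to 1 September 2026 = 1 day = 0.1 weeks; 1 July to 1 September 2026 = 62 days = 8.9 weeks.
- The Methods say one month for each sequence. The experimental dates exceed that throughout.

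**The case against.** The strongest reply is that the Methods already tie the assessments to the intervention: pre-test before the start, post-assessment at the end of the sequence, follow-up counted from the end of both interventions. On that view Project development stages is only a planning timetable, and the section on implementation risks allows an extension if there is delay. This stands in part. A reader might infer that patients will be post-tested in mid-treatment, but that follows only if the calendar overrides the Methods. The first age group could still be assessed between 10 and 31 August. The extension clause does not help, though: it covers delay, and these dates conflict with no delay at all.

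A reader might also infer that time since treatment is confounded with group in the 2x3 analysis. The documents do not establish this. The waiting-list dates after August 2026 belong to the phase in which those patients are themselves treated, and the protocol does not say which of their visits form the control arm. For the comparison of the two treatment sequences, both share the same dates within a wave, so the calendar creates no imbalance between them.

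It is also tempting to quote one range of 2.5-5 months for the experimental follow-up. That joins two incompatible end dates: the printed 31 July, and a full 168 days after a delayed start (16 September). Setting that range against the waiting list's printed end date would also apply the stagger to one wave only. The table above uses one rule for both.

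Finally, the conflict may come from a single wrong date. Purely as an illustration, a sequence starting on 1 January 2026 would end on 11 June, or 12 July with the stagger. December would then be 173-203 days (5.7-6.7 months) or 142-172 days (4.7-5.7 months) later. The document does not show which entry is wrong, and this review does not choose.

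**Conclusion.** The contradiction is real and shows at the level of whole months. The experimental window is 21.9 weeks at most against 24 weekly sessions plus a month's stagger. No March start followed by 24 weekly sessions is more than 4.7 months old by the end of December 2026. The experimental pre-test precedes 1 March by at least 8.6 weeks.

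The exact ranges rest on assumed first-of-month starts. With a later March start the experimental follow-up would be shorter still. With a later September start the waiting list would not overlap the delayed experimental group, but its own overrun past February would grow.

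The reach is limited. The follow-up error touches only the secondary questionnaires (BRIEF-2, BASC-3, BPI, AIQ, PROMIS); no primary performance test is listed for that visit. It still matters, because six months is a model level and a regression outcome, and the two waves would carry different intervals under that label. Whether the group comparison is biased depends on which waiting-list visits enter the model, which the protocol does not state.

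**What to change.** Reconcile Methods items 3, 4 and 6 with Project development stages, leaving the intervention as it is and without presuming which date is wrong. State explicitly that assessments are timed from each patient's own sessions:
- pre-test within one fixed window before the first session;
- post-assessment only after the last session;
- follow-up 6 months after the last session, with the same tolerance window in both waves.

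Reissue the calendar on that basis, showing both age groups. Record the actual days since last session and use them in the follow-up analysis.

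The cost is a revised timetable and possibly some moved hospital visits for pre- and post-assessment. The follow-up itself is by electronic questionnaire. Slack before the November-December 2027 analysis shrinks. If, for illustration only, the waiting list began on 1 October 2026 with its delayed group on 1 November, that group's last session would fall on 11 April 2027 and its 6-month visit on about 11 October 2027. That is still before the analysis, but only by about three weeks.
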